1.0 Objectives

1.1 Study Objectives

The central hypothesis of the research study is that low dose naltrexone (LDN), in combination with hormonal suppression of endometriosis (standard of care), will lead to significant improvement of endometriosis-related pain. The proposal seeks to: 1) determine if the addition of LDN to standard endometriosis treatments will improve patient- reported endometriosis associated pain using daily 100-point Visual Analogue Scale (VAS) scores and 2) measure the impact of treatment on quality of life as measured by questionnaires including the Endometriosis Health Profile-30 (EHP30) and the Patient's Global Impression of Change (PGIC), and Patient Global Assessments (PGA) specific to pain, dysmenorrhea, and non-menstrual pelvic pain. We propose a double-blind placebo-controlled randomized clinical trial to achieve the following aims:

Aim 1: Identify the impact of LDN on daily endometriosis associated pain. We hypothesize that LDN in combination with standard hormonal suppression of endometriosis will decrease endometriosis associated pain reported using the VAS as compared with hormonal suppression alone.

Aim 2: Identify the impact of LDN on quality of life among women with endometriosis. The EHP30 and PGIC are surveys used to measure quality of life outcomes. We hypothesize that LDN in combination with standard hormonal suppression of endometriosis will improve quality of life as compared with hormonal suppression alone

1.2 Primary Study Endpoints

The primary study endpoint is the difference in endometriosis associated pain as reported in daily VAS between study groups.

1.3 Secondary Study Endpoints

The secondary study endpoints will include the following quality of life measures:

- 1) Patient's Global Impression of Change (PGIC) surveys
- 2) Endometriosis Health Profile-30 (EHP 30) surveys
- 3) Patient Global Assessment (PGA)- pain, dysmenorrhea, non-menstrual pelvic pain

Additional secondary outcomes will include pain medication use (opioid and non-opioid). Subject reported daily analgesic use (NSAIDs and opioid) will be recorded and narcotic prescriptions will be verified using the state run Prescription Drug Monitoring Program monthly. Subject reported side effects to medications will also be monitored.

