3.2 Exclusion Criteria

Exclusion

- Women that are pregnant, breastfeeding or trying to conceive.
- Patients with chronic daily opioid use and any chronic pain or frequently reoccurring pain condition, other than endometriosis, that is treated with opioids or requires analgesics for more than 7 days per month.
- Patients with abnormal liver function tests (greater than 3x normal limit) in the past year or history of liver disease. Routine screening of liver function is not required.
- Non-English speaking or inability to read and understand English secondary, in part, to the need to read and report daily results in English.
- Undiagnosed vaginal bleeding
- Patients with history of opioid, illicit drug or alcohol abuse
- Patients currently taking thioridazine
- Patients with a history of suicidality
- Patients with current or history of unstable depression or other psychiatric disorder who, by PI judgement, are unstable or not well controlled
- Known, suspected or history of cancer of the breast
- Active deep vein thrombosis, pulmonary embolism or history of these conditions
- Active or recent arterial thromboembolic disease (e.g., stroke, myocardial infarction)

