4.4 Eligibility/screening of subjects

When the study team receives information about a potential subject, follow-up is made to verify eligibility. If excluded, no further questions are asked and they are thanked for their time. If eligible the subject is scheduled for a visit.

Follow-up includes a phone screen of the potential subject by asking questions such as, ensuring the subject is premenopausal and in between the ages of 18 and 45 years old, agree to only use study-specific analgesic medications during the study and if intolerance to oxycodone and ibuprofen are known, agrees to use Norethindrone acetate and either their LARC or other barrier contraception while in the study, if the subject plans on becoming pregnant or trying to conceive at any point during the study, if the subject has any chronic daily narcotic use and any chronic pain other than endometriosis, and verify the subject is able to speak and read English to answer the surveys. We will also confirm that the subject is willing and able to be reliably contacted by email for study specific purposes.

If the participant passes the phone screen, the participant will be scheduled for a screening visit. After consent and receiving Norethindrone acetate, an email will be sent for the subject to complete the daily surveys for next 6-7 days. Upon completion of the surveys, the participant will pass or fail the screening process.

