7.0 Study Design and Procedures

7.1 Study Design

We propose to conduct a randomized double-blind placebo-controlled trial to evaluate the effectiveness of low-dose naltrexone (4.5 mg daily) in combination with a standard treatment (norethindrone acetate daily) on management of endometriosis-associated pain. Potential subjects will be screened in the Penn State Minimally Invasive GYN Surgery clinic for endometriosis-associated pain for greater than 6 months. Subjects will be screened from new and existing patients in the Minimally Invasive GYN Surgery clinic as well as from referral sites including surrounding general OBGYN and Primary Care practices. Those meeting all inclusion and exclusion criteria that are willing to participate will receive a detailed history and physical exam. Baseline survey data will be collected and entered into the RedCap secured database. At this time subjects will be set up for daily emails to complete VAS scores directly into RedCap. The first visit will be scheduled 1 week following the screening visit.

During the first visit subjects will be screened for daily reporting compliance. Subjects having completed 5 or fewer daily VAS scores and surveys during the baseline collection will be offered one additional 7-day period to improve compliance. If at the conclusion of the second 7-day run-in period of gathering daily baseline VAS scores and survey responses they continue to have 5 or fewer entries per week they will be considered a screen failure and withdrawn from the study. Those subjects meeting the 6 entry or more threshold of daily reporting at either visit 1 or following the second 7 day run in period will be randomized in the study.

Randomized subjects will receive norethindrone acetate 5 mg (up to 15 mg depending on subject's needs) daily plus LDN 4.5 mg daily or norethindrone acetate 5 mg (up to 15 mg) daily plus placebo. If the subject is taking norethindrone acetate prior to the study, she will remain on her current dose to start the study. Dose adjustments will be made, if needed, to achieve amenorrhea or minimize uterine bleeding. Menstrual status will be assessed and documented in a progress note if this should occur either in person at a study visit or via telephone in the interim. Norethindrone acetate is provided in 5mg tablets; if dosing adjustment is needed, the study staff will arrange to ship additional study drug via FedEx.

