Pre-screening will take place over the phone with women identified as potential candidates for study participation via clinic visits or other previously discussed methods of subject recruitment. Initial contact will be made via the telephone to assess women's interest in participation. As per standard of care, narcotic usage is assessed during routine clinic visits.

If the subject meets all pre-screening criteria, the subject will be scheduled for a screening visit. At the screening visit, the informed consent will be reviewed and the subject will be given ample time to ask any questions or concerns about the study. Once informed consent is signed, the subject information will be placed in redcap and a test email will be sent to the subject. Those meeting all inclusion and exclusion criteria that are willing to participate will receive a detailed past medical history and physical exam. Baseline surveys and any adverse events will be collected and entered into the RedCap secured database.

The subject will complete the WERF survey, VAS score, EHP-30 and PGAs during the visit to ensure understanding and allow the coordinator to help with any questions. The subject will be given a 2 week supply of Norethindrone acetate to start during the run-in period and given instruction on how to complete the daily VAS scores and study questions. It will be explained to the subject that they must complete at least 6 out of the 7 days of surveys to be enrolled into the study. If the subject is unable to complete the 6 out of 7 days of surveys, the subject will be given one additional week to determine if compliance is attainable. (This will ensure provide ample opportunity for

enrollment for potential subjects with unpredictable barriers to completion in the first 7 days.) If the subject is unable to do so, they will be a screen fail. Those completing greater than or equal to 6 entries in either of the 7-day periods will be eligible for enrollment in the study. In the event of needing an additional 7-day run-in period, data points during the screening period will **not** be assessed in aggregate for eligibility.

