7.2.2 Study Visit 1: Randomization/ Enrollment

The subject will be scheduled for a randomization/enrollment visit one week after the screening visit. At this visit, the subject will be randomized into group A or B by IDS as long as the subject has met all the criteria for enrollment. This study will compare low dose naltrexone with a placebo, or sugar pill. Both study groups will receive norethindrone acetate for treatment of their endometriosis during the study period. Dosing for norethindrone acetate will be 5 mg to 15 mg depending on the subject's needs and will be adjusted as needed to achieve amenorrhea or minimize uterine bleeding as this standard treatment for endometriosis. The 2 groups are listed below:

Group	Treatment
Α	Norethindrone acetate (daily) + Placebo (4.5 mg daily)
В	Norethindrone acetate (daily) + Naltrexone (4.5 mg daily)

The subject will be given 1-month supply of Norethindrone acetate and 1-month (30 day) supply of study medication and instructed to take it once a day. The subject will take the first dose of study drug in clinic with study personnel present.

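### No independent check of opioid use is stated before randomisation to a blinded opioid antagonist, although the trial already has the means to make one

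*Combined protocol and SAP*

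**What the plan says.** Section 3.2 has two opioid exclusions. The first begins "Patients with chronic daily opioid use and any chronic pain or frequently reoccurring pain condition, other than endometriosis, that is treated with opioids"; the second is "Patients with history of opioid, illicit drug or alcohol abuse".

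The phone screen in 4.4 asks "if the subject has any chronic daily narcotic use and any chronic pain other than endometriosis", and 5.1.2 repeats the question. Section 7.2.1 adds: "As per standard of care, narcotic usage is assessed during routine clinic visits". Sections 5.1.2 and 6.2.2 provide for reading the medical record before consent to find eligible women, and 7.1 and 7.2.1 provide for a detailed history and physical examination.

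The visit table in 7.1 schedules the daily pain and analgesic assessment for 6 to 7 days of run-in. The rule for leaving the run-in is stated in entries: "Those subjects meeting the 6 entry or more threshold of daily reporting" are to be randomised (7.1), and 7.2.1 says the same of eligibility. Section 7.2.2 then randomises a woman provided that she meets all enrolment criteria, and adds: "The subject will take the first dose of study drug in clinic with study personnel present".

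The prescription-monitoring query appears once, in 1.3, where it supports the pain-medication outcome: "narcotic prescriptions will be verified using the state run Prescription Drug Monitoring Program monthly".

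**The concern.** Sections 2.1 and 2.3 describe naltrexone as a competitive opioid antagonist that, at low dose, transiently blocks all three opioid receptor subtypes. The opioid exclusions are therefore safety criteria, and they protect a woman only if someone checks them before her first dose.

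For the outcome, the sponsor judged that self-reported opioid use needed an outside source. No such source is stated for entry, where the answer decides whether a woman may be given a blinded antagonist. The trial also collects a week of analgesic reports before randomisation and states no rule that uses them. At stake is whether the sponsor's own exclusion is enforced as well as the trial's existing tools allow.

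**Working it through.** This point rests mainly on setting the steps before the first dose side by side.

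| Step | Where | Does it bear on opioid use? | Written as a check of 3.2? |
|---|---|---|---|
| Phone screen | 4.4, 5.1.2 | Yes, by self-report. Abuse history is not among the listed examples, though the list is not presented as complete | It asks, but does not verify |
| Medical record review | 5.1.2, 6.2.2 | Could do; no opioid item named | No |
| Routine clinic assessment | 7.2.1 | Yes, as standard care | No |
| History and examination | 7.1, 7.2.1 | Could do; no opioid item named | No; described as following once the criteria are met |
| Concomitant medication record | 7.4.6.5 | Yes | No |
| Run-in diary | Visit table, 7.1, 7.2.1, 4.4 | Yes, daily and self-reported | No; only completion counts |
| Confirmation at Visit 1 | 7.2.2 | All criteria must be met | No source named |
| Prescription-monitoring query | 1.3 | Yes, independent of the woman's report | No; stated for the outcome, monthly, no start date |

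The run-in rule is 6 of 7 entries, and 6/7 = 85.7%, which agrees with the 85% compliance in 8.1. It is a rule about reporting. A diary with seven entries that each record an opioid satisfies it just as one that records none.

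**Is the sample size affected?** Inputs from 8.2: difference 10 mm, SD 20 mm (ratio 0.5), two-sided 0.05, 80% power, 20% withdrawal.

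- Normal approximation: n = 2 × (1.960 + 0.842)² / 0.5² = 62.8, so 63 per arm. 63/0.8 = 78.75, so 79 per arm and 158 in all.
- t-test: 63.77, so 64 per arm. 64/0.8 = 80 per arm and 160 in all, the plan's figure.

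A check made before randomisation changes none of these inputs, so 160 stands.

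**How many women might be involved?** The documents give no rate of undisclosed regular use. Let p be the assumed share among randomised women. With 80 on naltrexone, the expected number is 80p and the chance of at least one is 1 − (1 − p)^80.

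| Assumed p | Expected among 80 | Chance of at least one |
|---|---|---|
| 0.5% | 0.4 | 1 − 0.995^80 = 33% |
| 1% | 0.8 | 1 − 0.99^80 = 55% |
| 2% | 1.6 | 1 − 0.98^80 = 80% |

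These are illustrations, not estimates. Two figures in the protocol look usable and are not. The 56.3% in 2.2 counts any narcotic fill in the two years after diagnosis in a claims population, whereas 3.1 admits diagnoses up to 10 years old and the trial screens its entrants. The 3% to 4% in 2.1 is all long-term therapy among US adults.

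**The case against.** The strongest reply is that the plan already requires what is asked. Section 7.2.2 randomises only women who meet every criterion, so one whose known use meets 3.2 is ineligible however many diary entries she made. The entry count is an added compliance requirement and does not replace eligibility. Records, clinic assessment, history and the concomitant medication list all give staff a chance to find opioid use, and a surgical diagnosis within 10 years (3.1) means that some record exists for every woman. Protocols often do not name a source for each criterion.

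Much of this stands. A reader might infer that the exclusions are settled by self-report over the phone; the other steps show that this goes too far. A reader might also infer that the query is never run before randomisation. The documents say only that it is monthly, so the supportable statement is that an earlier query is not stated.

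A third tempting inference is that undisclosed users would react, withdraw or be unmasked in the naltrexone arm only and so bias the comparison. The documents do not show that 4.5 mg has this effect. They describe incomplete, transient blockade (2.1, 2.3), and section 11 says no interactions of the low dose with other medications are reported. That is no evidence of safety in opioid users, but it leaves the bias argument without support here.

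The proposed check also has limits. The diary is self-report, and seven days cannot establish chronic use. The query shows dispensed prescriptions, not intake. Neither is shown to capture abuse history. Section 7.2.2 allows oxycodone on request, so an opioid entry is not by itself an exclusion.

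The reply does not answer why the one independent source the trial has is tied only to the outcome, or why a week of analgesic reports has no stated use when eligibility is confirmed.

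**Conclusion.** The point holds as a low-cost improvement to conduct. It is not an error in the analysis or the sample size. No independent opioid check is stated before randomisation, and the run-in rule does not use the analgesic content of the diary. A regular opioid user who did not disclose this could therefore reach a blinded antagonist at Visit 1 without any written step designed to find her.

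No magnitude is claimed. The 33% to 80% chance of at least one such woman on naltrexone depends wholly on the assumed 0.5% to 2%, for which the documents give no basis. In particular, multiplying 56.3% by 160 to get about 90 women with a recent opioid history would be wrong, because that figure describes neither recent nor regular use in screened women. No effect on the primary comparison has been shown.

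A separate matter bears on how any check is read. The *and* in the first exclusion can be taken to require both daily opioid use and another pain condition. Rewording it would not supply the missing check, and adding the check would not settle the wording.

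**What to change.** In 7.2.1, 7.2.2 and the visit table, state that:

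- the first prescription-monitoring query is run after consent and before randomisation, with the monthly queries following as in 1.3;
- the opioid entries of the run-in diary are reviewed against 3.2 as part of confirming under 7.2.2 that all criteria are met, whatever the number of entries;
- a named role signs off that both were done before the first dose.

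The sponsor should reconcile what counts as meeting the opioid exclusion, including its *and* wording, and how reported run-in use is read against it. No threshold or interval is proposed here.

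The cost is one extra query per consented woman with a tool already in use, a look at data already collected, and a few more screen failures. The planned 160 does not change. The check would narrow the gap without closing it: opioids that were not dispensed on prescription and not reported would still be missed.

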2.0 Background

2.1 Scientific Background and Gaps

Endometriosis is a significant public health problem. It is estimated to occur in 6-10% of the general female population.^{1,2,13} It is defined as the presence of endometrial glands and stroma located outside of the intra-uterine cavity.^{2,14} The primary symptoms of endometriosis are debilitating, cyclic pelvic pain and infertility.^{3,4} The prevalence of endometriosis among women with pelvic pain or infertility increases to 40% when compared to their healthy peers. Some experts suggest that endometriosis is present in over 70% of women with chronic pelvic pain.

The exact cause of endometriosis remains unknown; however, the major mechanism is thought to be retrograde menstruation, otherwise known as Sampson's Theory.^{1,2} During menses the uterine lining, known as the endometrium, breaks down and begins to separate from the muscular portion of the uterine cavity. This process results in bleeding. The muscular portion of the uterus then contracts and expels the endometrial tissue and blood through the cervix into the vagina and out of the body. For many women, a small amount of endometrial tissue and blood is expelled in a retrograde fashion through the fallopian tubes and into the abdominal cavity.^{1,2} The blood and endometrial tissue then settle into the dependent parts of the pelvis. This theory is consistent with the clinical presentation of endometriosis, as the most common locations of endometriosis are the ovary, the recto-vaginal space, the pelvic sidewall along the course of the ureter and the bladder surface.^{1,2}

Endometriosis implants, although small, can have a major impact on the quality of life for many women. Endometriosis is associated with pain that is disproportionate to cellular injury and seems to be hyper responsive to inflammatory processes.^{1,2,14} In addition, they are responsive to the changes in hormone levels, particularly estrogen and progesterone, which fluctuate during the menstrual cycle.^{1,2,4} These hormonal changes along with the significant inflammation that occurs immediately before and during menses play a large role in the symptoms of debilitating pain experienced by women. Some women experience similar symptoms during other clinical situations leading to inflammation in their pelvis. For example, constipation, diarrhea, or bladder infections are some of the many other causes of significant pain in endometriosis patients.

There are many challenges in the diagnosis and management of endometriosis. Current standards require surgery with either pathologic confirmation of biopsied lesions or direct visualization of "classic" appearing lesions for diagnosis. Endometriosis is not visualized via any current imaging techniques. Blood, urine and other body fluid evaluation cannot provide a diagnosis either. The invasive nature of diagnostic testing often leads to a delay in diagnosis of 6-11 years among women, including those with symptoms highly suggestive of endometriosis. Unfortunately, this leads to delays in treatment.

Given the frequent delays in diagnosis, many women also have narcotic pain medications incorporated into their treatment plan secondary to the severity and recurrent nature of endometriosis-associated pain.^{1,3,9,15} This often occurs with or without a formal diagnosis of endometriosis. Currently, I work at a regional referral center for the management of endometriosis. Many patients present to our clinic already have been exposed to narcotic pain medications prior to their initial consultation.

Current literature reports that in 2014 alone US retail pharmacies dispensed 245 million prescriptions for opioid based narcotic pain relievers.¹⁵ Three to four percent (9.6-11.5 million) of the adults in the US population are prescribed long-term opioid therapy.¹⁵ Currently, there are no published data evaluating the utilization of long-term opioids in the endometriosis population. Secondary to this knowledge gap we evaluated data from a national, longitudinal, claims-based database to evaluate opioid use in endometriosis patients. We identified 706, 863 women meeting inclusion criteria that had the diagnosis of endometriosis and also had at least 1 year of continuous data prior to and 2 years of continuous data following the diagnosis of endometriosis. We found several strong correlations between endometriosis and opioid use. Among women with endometriosis not only was there a significant increase in the percentage of subjects getting a prescription for opioids (56.3% vs 34.5%) in endometriosis patients vs. controls, but women with endometriosis who received opioids were more likely to receive multiple prescriptions and had a higher median cumulative dose of opioids that their matched controls (manuscript in preparation). Due to the growing opioid epidemic and the limited effective treatments for endometriosis related pain, there is a dire need to understand

the extent of opioid utilization in this patient population. We must continue to work to develop effective non-opioid based treatments that alleviate endometriosis-associated pain symptoms and decrease the use of narcotic pain medications for endometriosis.

Naltrexone is an opioid antagonist that is FDA approved for the treatment of opioid and alcohol dependence. Naltrexone is thought to act through competitive antagonism at the level of opioid receptors in the central nervous system.^{6,5} Naltrexone is absorbed orally and metabolized into its active metabolite 6-beta-naltrexone during its first pass through the liver.⁵ It is widely distributed throughout the body giving it great bioavailability. Naltrexone is primarily excreted in urine.⁵ There is emerging evidence that when used at a significantly reduced dose (approximately 1/10 the dose traditionally prescribed), naltrexone has different pharmacologic effects.^{6,5} Low dose naltrexone (LDN) has been used and studied in other chronic conditions. Most of the data are related to multiple sclerosis, Crohn's disease, and fibromyalgia.^{6,5} Current literature reports that LDN is well tolerated with minimal side effects. The most common side effect reported was vivid dreams.⁵ There is still a significant lack of randomized controlled trials for LDN use in any condition; however, both animal and human studies have demonstrated promising results.

LDN is thought to function through multiple different mechanisms that would be expected to benefit women suffering with the chronic symptoms of endometriosis-associated pain. Three of these mechanisms will be discussed here. First, LDN causes upregulation of opioid receptors and increased endogenous opioid production.^{6,5,12} Second, it blocks toll-like receptor 4 (TLR4) in glial cells found in the central and peripheral nervous system. Finally, LDN has been demonstrated to impact the production of peripheral inflammatory cytokines.

[name] and team have done significant amounts of work in this area using rodent models. Their hypothesis of the mechanism of action of LDN is that is causes transient and incomplete blockade of opioid receptors. This phenomenon has been demonstrated with both naltrexone and naloxone in multiple studies. The consequence of exposure to LDN has been referred to as an opioid rebound effect. This leads to improved endogenous analgesia through increased opioid production and sensitivity.^{6,5,12,16,17} The concept of inducing a paradoxical effect with variable doses of medication acting at opioid receptors is not novel to naltrexone; in fact it has been demonstrated previously with low-dose morphine. Multiple previous studies have also demonstrated hyperalgesia in rats when exposed to morphine as low doses.⁵ The effect was routinely described at doses around 1/10 the standard dose given to treat pain. The paradoxical effects of naltrexone also seem to present as doses around 1/10 the standard treatment doses.⁵

It is well know that inflammation is a key component in endometriosis-associated pain.^{1,2} Nonsteroidal anti-inflammatory medications are considered first line treatment for endometriosis, but often fall well short of providing adequate pain control.^{3,4} Evidence suggests that women with endometriosis can be thought of as having a pelvic inflammatory condition.² Additionally, endometriosis lesions are associated with increased peritoneal vascularity and innervation.² This is thought to play a significant role in pain. It is hypothesized that the combination of increased nerve density along with recurrent inflammatory processes in the female pelvis (e.g. menses) cause devastating symptoms often presenting similar to neuropathic pain.^{1,2,14} The evidence that LDN has antagonistic effects on TLR4 in the glial cells suggests that it could be an ideal medication choice for endometriosis-associated pain.^{6,5} Activation of the microglia in the central nervous system has been shown to increase inflammatory and excitatory factors leading to pain sensitivity as well as other symptoms. To the contrary, opioids have been shown in previous studies to stimulate TLR4 activity leading to opioid induced inflammation.^{6,5} This may be one explanation as to why opioid therapy has not demonstrated improved outcomes with chronic use in endometriosis or other chronic inflammatory conditions such as fibromyalgia. These data are further supported by other studies performed using dextro-naltrexone. This stereoisomer of naltrexone is active at the glial cell and not at the opioid receptor. Dextro-naltrexone demonstrated both analgesic and neuroprotective properties.⁵

Most research demonstrating the general anti-inflammatory effects of LDN have been completed in animal models, but there are some pilot studies demonstrating this effect in humans as well. Multiple pilot studies have demonstrated decreased levels of inflammatory markers in women with fibromyalgia following administration of LDN.^{5,7,18} Fibromyalgia (similar to endometriosis) is considered an inflammatory disorder. One study demonstrated that women with fibromyalgia and an elevated erythrocyte sedimentation rate (ESR), which is a serum marker for inflammation, had improved response rates to LDN as compared to women with fibromyalgia and a normal ESR.⁷ A separate 10-week crossover trial using LDN in women with fibromyalgia demonstrated significantly decreased plasma concentrations of multiple key pro-inflammatory cytokines as well as a 15% reported decrease in fibromyalgia associated pain.¹⁸

In summary, endometriosis is a devastating disease that impacts nearly 1:10 women in the reproductive years or their life. The pathophysiology of endometriosis is not completely understood, however, there is strong evidence that inflammation plays a major role in the symptoms associate with endometriosis. Current strategies for the management of endometriosis-associated pain often leave women seeking additional relief in the form of opioid-based treatments. In light of the current opioid epidemic it is important that we continue seek non-opioid based therapies that can provide symptomatic relief while we continue to try and better understand this debilitating disease. LDN has gained some popularity as an off-label treatment for inflammatory conditions such as multiple sclerosis, Crohn's disease and fibromyalgia, but the literature has nothing to offer in the way of significant randomized controlled trials to adequately test the mounting evidence that LDN is beneficial in chronic inflammatory conditions to include endometriosis.

